4.5 SAFETY ANALYSES

The SAS and the ocrelizumab exposed analysis set are described in Section 3. All safety parameters will be summarized and presented in tables on the basis of these analysis sets.

The baseline is defined as the last available assessment prior to the first study drug administration for the safety analysis set and as the last available assessment prior to the first ocrelizumab administration [study drug, post-double-progression ocrelizumab (PDP OCR), or commercial ocrelizumab] for the ocrelizumab exposed analysis set.

For the safety analysis set, the safety data will be summarized from the first study drug administration until when patients receive any PDP OCR, open-label extension ocrelizumab (OLE OCR), commercial ocrelizumab treatment, or other MS DMT. In addition, the adverse event (AE) profile will be summarized in the following subgroups:

- Age > 55 versus ≤ 55
- EDSS score ≤ 6.5 versus > 6.5
- MRI-inactive versus MRI-active
- Males and females
- Treated prior to randomization with another DMT for MS

For the ocrelizumab exposed analysis set, the safety data will be summarized from the first ocrelizumab administration (study drug, PDP OCR, OLE OCR or commercial ocrelizumab) until when patients receive any other MS DMT.

In an exploratory analysis, the AE profile will be summarized using data collected from the first ocrelizumab administration until the end of the study. Every effort will be made to collect the safety data until the end of the study.

Safety will be assessed through summaries of exposure to study treatment, AEs, changes in laboratory test results, and changes in vital signs. All verbatim AE terms will be mapped to Medical Dictionary for Regulatory Activities (MedDRA) thesaurus terms, and AE severity will be graded according to National Cancer Institute Common

Terminology Criteria for Adverse Events (NCI CTCAE) v5.0. All AEs, serious adverse events (SAEs), AEs leading to death, AEs of special interest, and AEs leading to study treatment discontinuation that occur on or after the first dose of study treatment (i.e., treatment-emergent AEs) will be summarized by mapped term, appropriate thesaurus level, and severity grade. For events of varying severity, the highest grade will be used in the summaries. Deaths and cause of death will be summarized. Relevant laboratory and vital sign (pulse rate and blood pressure) data will be displayed by time, with grades identified where appropriate. Additionally, a shift table of selected laboratory tests will be used to summarize the baseline and maximum post baseline severity grade. Changes in vital signs will be summarized.

4.5.1 Extent of Exposure

Study treatment exposure such as treatment duration, total dose received, and number of doses and infusion modifications will be summarized with descriptive statistics.

4.5.1.1 Details in Defining the Number of Doses and Total Dose Received

The first dose is given as two infusions administered 2 weeks apart. If a patient receives any infusion at Dose 1, the patient is counted as having received the first dose.

If a dose is completely missed instead of delayed, the next dose number will be consecutive to the previous dose received.

4.5.1.2 Treatment Duration and Duration under Observation Definitions

Treatment duration during the DBT and FU1 phases will be calculated as follows:

(Date of the last recorded treatment observation during the DBT and FU1 phases* – Date of first dose of the DBT phase) + 1

*The date of the last recorded treatment observation during the DBT and FU1 phases is defined as the earliest between:

- date of last dose received during the DBT phase + 24 weeks
- last day prior to entering in FU2 as per the subject disposition eCRF page
- last day prior to the first OLE dose
- last day prior to the first PDP OCR dose
- last day prior to start of commercial ocrelizumab treatment or other MS DMT
- clinical cutoff date (CCOD) for the primary analysis reporting
- date of discontinuation from the study as indicated on the subject disposition eCRF page
- date of death

Treatment duration for all ocrelizumab exposed patients will be calculated as follows:

(Date of the last recorded treatment observation for all ocrelizumab exposed patients*–Date of the first dose of ocrelizumab (study drug, PDP OCR, OLE OCR or commercial ocrelizumab))+ 1

*The date of the last recorded treatment observation for all ocrelizumab exposed patients is defined as the earliest between:

- date of last dose of ocrelizumab (study drug, PDP OCR, OLE OCR or commercial ocrelizumab)+24 weeks
- last day prior to start of other MS DMT (not including commercial ocrelizumab)
- date of discontinuation from the study as indicated on the subject disposition eCRF page
- CCOD for the primary analysis reporting
- date of death

The duration under observation during the DBT and FU1 phases for a patient will be calculated as follows:

(Date of last observation during the DBT and FU1 phases*–Date of first infusion in the first dose)+ 1

*Date of last observation during the DBT and FU1 phases is defined as the earliest between:

- the latest recorded date in all CRF and non CRF data prior to CCOD
- last day prior to entering in FU2 as per the subject disposition eCRF page
- last day prior to the first OLE dose
- last day prior to the first PDP OCR dose
- last day prior to start of commercial ocrelizumab treatment or other MS DMT
- date of discontinuation from the study as indicated on the subject disposition eCRF page
- date of death

The duration under observation for all ocrelizumab exposed patients will be calculated as follows:

(Date of last observation for all ocrelizumab exposed patients* –Date of first infusion in the first dose of ocrelizumab)+ 1

*Date of last observation for all ocrelizumab exposed patients is defined as the earliest between:

- the latest recorded date in all CRF and non CRF data prior to CCOD

- last day prior to start of other MS DMT (not including commercial ocrelizumab)
- date of discontinuation from the study as indicated on the subject disposition eCRF page
- date of death

The duration of observation, within a dose, is defined in a similar manner as follows:

$(\text{Day prior to first infusion in the } n+1\text{th dose}^* - \text{Date of first infusion in the } n\text{th dose}) + 1$

*With the exception of the last dose received by the patient where the date of last observation during the DBT and FU1 phases or for all ocrelizumab exposed patients is used as defined above.

4.5.2 Adverse Events

AEs will be defined as all AEs including infusion-related reaction (IRRs) and serious MS relapses, but excluding non-serious MS relapses. Therefore, those AEs recorded on the AE and IRR CRF pages will be included.

For each recorded AE, the term entered by the investigator describing the event (the “reported term”) will be assigned to a standardized term (the “Preferred Term” [PT]) and assigned to a superclass term on the basis of the MedDRA World Health Organization (WHO) dictionary of terms. All analyses of AE data will be performed using the PTs unless otherwise specified.

For all summary tables, the AEs will be sorted by System Organ Class ([SOC]; in decreasing order of overall incidence) and then by PT (in decreasing order of overall incidence). Summaries of AEs will be generated to summarize the incidence of treatment-emergent AEs only. Treatment-emergent events are defined as those AEs with an observed or imputed date of onset on or after the start date of trial treatment or with CRF flag “Event occurred prior to first study drug administration” equals “no”. If the onset date of the AE is prior to the day of first dose, the AE will be considered treatment-emergent only if the most extreme intensity is greater than the initial intensity (i.e., the intensity for a given AE increases and its end date is on or after the date of the first dose). An AE with a completely missing, non-imputed start date will be assumed to be treatment emergent unless the AE has a complete, non-imputed end date that is prior to the date of the first dose.

AEs will be assigned to a dose if the AE onset date is on or after the date of the first infusion of that dose but before the first infusion of the next treatment dose. AEs that are reported during non-dosing phases (Follow-up 1, Follow-up 2) will be assigned to the last dose received. AEs that start prior to the first dose and worsen during treatment (i.e., treatment-emergent) will be assigned to the first treatment dose.

The number of patients who experienced a related AE will be summarized by SOC and PT. AEs will be summarized by SOC and PT by intensity grade. Multiple occurrences of the same event within a patient will be counted once at the greatest intensity/highest grade for this PT. For AEs leading to death, the most extreme intensity will be overwritten by Grade 5 (death). Any AEs and the SOC overall rows of the summary table will count patients according to AEs by intensity (grade).

All patient deaths will be listed.

SAEs will be defined as all SAEs including serious MS relapses and serious IRRs. The number of patients who experienced an SAE will be summarized by SOC and PT. Related SAEs will be summarized by SOC and PT. Additionally, the most frequent SAEs ($\geq 1\%$) will be presented by SOC and PT.

Clinical relapse will be considered an SAE when the relapse results in hospitalization for any reason other than routine treatment of the relapse (e.g., for a treatment course beyond the standard treatment described or when hospitalization is prolonged). These events will be listed and summarized.

A patient may experience an AE that leads to withdrawal from study treatment. Withdrawal from study treatment for an AE may not necessarily lead to withdrawal from the study. Only AEs that led to study treatment withdrawal are of interest. Patients who withdraw early from the study because of AEs will be summarized under disposition. The number of patients who experienced an AE that led to study treatment withdrawal as well as the number of patients who experienced an AE that led to modification or interruption of study drug will be summarized by SOC and PT. The number of patients previously treated with an another DMT for MS who experienced an AE will be summarized by SOC and PT.

For each treatment group, the incidence count for each AE PT will be defined as the number of patients reporting at least one treatment-emergent occurrence of the event. The incidence rate will be calculated as the incidence count divided by the total number of patients in the population. Each table will also present the overall number of patients experiencing at least one AE and the total number of AEs reported.

The rate per 100 patient-years by treatment group (along with the 95% CI) will be calculated for specific events of interest such as all AEs, SAEs, infections and serious infections (see Section 4.5.4), opportunistic infections ([OIs]; see Section 4.5.5), and malignancies (see Section 4.5.6).

- The number of AEs per 100 patient-years is calculated as:
 $(\text{Total number of AEs} \div \text{Total number of patient-years}) \times 100$

- The 95% confidence interval (CI) for the number of AEs per 100 patient-years will be calculated using the exact method based on the Poisson distribution (Sahai and Khurshid 1993):

Exact lower 95% confidence limit = $\text{chisq}(p = 0.025, df = 2Y) / (2T)$

Exact upper 95% confidence limit = $\text{chisq}[p = 0.975, df = 2(Y + 1)] / (2T)$

where Y is the total number of AEs, T is total number of patient-years at risk and $\text{chisq}(p, df)$ is the quantile of the upper tail probability of the Chi-squared distribution with df degrees of freedom. This approach has the advantage of providing an estimate for the upper 95% confidence limit even when the total number of AEs is zero.

The rates per 100 patient-years will be summarized by treatment and dose and by treatment (including all doses).

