1.2 STUDY DESIGN

Study WA40404 is a Phase IIIb, randomized, double-blind, placebo-controlled, parallel-group, multicenter study to evaluate efficacy and safety of ocrelizumab administered at a 600 mg intravenous (IV) infusion every 24 weeks in patients with PPMS, including patients later in their disease course. This study will consist of the following phases: screening, double-blind treatment, an optional

post-double-progression ocrelizumab (PDP OCR) treatment, follow-up 1 (FU1), an optional open-label extension (OLE), and follow-up 2 (FU2).

Patients providing informed consent will undergo screening prior to the study drug administration. Eligible patients will be randomized (1:1) in a blinded fashion to either placebo or ocrelizumab. Randomization will be performed through an interactive voice or web-based response system (IxRS).

The expected sample size will be approximately 1000 patients, with at least 350 patients in the magnetic resonance imaging (MRI)-active subgroup. The MRI-active subgroup will consist of patients with T1 Gd+ lesion(s) and/or new and/or enlarging T2 lesion(s) as detected by MRI scan during screening. If during the study conduct more than 650 patients have enrolled without MRI activity (referred to as MRI-inactive subgroup thereafter), then subsequently only patients with MRI activity may be enrolled to ensure that at least 350 patients with MRI activity will be randomized.

Patients will be treated for 144 weeks (6 study drug doses, with each dose 24 weeks apart) in the double-blind treatment phase or until the primary analysis, whichever occurs earlier. Patients who experience a double-progression event (DPE; defined as a confirmed 20% increase in 9-HPT time sustained for 24 weeks, and a CDP sustained for 12 weeks) during the double-blind treatment phase will be given the option to switch to PDP OCR after they have completed at least 120 weeks of double-blind treatment and 120-week visit assessments.

Patients will be recruited globally. Patients who prematurely discontinue from study treatment will continue to be followed in the FU1 phase until 144 weeks from randomization for each patient or until the primary analysis, whichever occurs earlier.

The primary analysis will be performed after the last randomized patient reaches the 144 weeks of double-blind treatment (+ 12 weeks to allow for the confirmation of the latest event) or when at least 340 events are reached, whichever occurs earlier.

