4. STATISTICAL ANALYSES

4.1 GENERAL CONSIDERATIONS

As per the EMA guideline on multiplicity issues in clinical trials (EMA, 2017) and the FDA guidance for industry on multiple endpoints in clinical trials (FDA, 2022) multiple primary endpoints are designated as co-primary endpoints if study success is defined by a positive outcome in all primary endpoints.

In this SAP, the terminology co-primary endpoint and co-primary estimand is used although study success is defined by a positive outcome in at least one of the two co-primary endpoints, analogous to multiple primary endpoints.

For all continuous variables for which descriptive statistics are reported, the following will be reported: the number of observations, the mean, median, standard deviation, and minimum and maximum. The 25th and 75th percentiles (Q1 and Q3) will also be reported for selected tables. Descriptive summaries of discrete data will include frequencies expressed in terms of number and percentage of patients.

All primary and secondary efficacy endpoints will be stratified by/adjusted for:

- MRI activity, defined as any T1 Gd+ lesion(s) and/or new and/or enlarging T2 lesion(s) during the screening period (yes vs. no)
- Age (≤ 55 . vs. > 55)
- EDSS score (≤ 6.5 vs. > 6.5)
- Region (two regions: European Union, United Kingdom, and Canada vs. other)

The baseline is defined as the most recent value prior to first dose administration (or up to and including the date of randomization for non-treated patients), unless specified otherwise.

The baseline MRI is defined as the most recent MRI prior to randomization.

For EDSS and 9-HPT, baseline is defined as the most recent value prior to randomization.

There will be no imputation of the baseline outcome value, with the consequence that participants missing the baseline outcome measure will not contribute to the analyses which use change from baseline of a given outcome measure as the dependent variable.

For analysis purposes, the time of treatment discontinuation will be defined as 24 weeks after the last dose prior to the date of treatment discontinuation recorded in the electronic Case Report Form (eCRF).

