4.5.4 Infections

Infections will be defined from the AE data using the MedDRA SOC of “Infections and infestations”. Infections will be classified according to the pathogen type (e.g., bacterial, fungal, viral, parasitological, unknown, or other).

An infection will be defined as serious if the event is an SAE as defined in Section 4.5.2. A listing will be presented of non-serious infections treated with an IV anti-infective.

The number of patients who experienced an infection will be summarized by SOC and PT and by intensity.

The number of infections experienced by more than 5% of patients will be summarized by SOC and PT.

The number of patients who experienced a serious infection will be summarized by SOC and PT.

Identified pathogen codes will not be summarized but will only be listed within the listings of infections and serious infections. Infections and serious infections will be summarized by pathogen types.

The rate per 100 patient-years by treatment group (along with the 95% CI) will be calculated for infections and serious infections overall and by dose based on the number of patient-years observation for the specific dose.

For infections and serious infections, the incidence rate ratio will be calculated. For these analyses, the incidence rate ratio with 95% CI based on the Poisson distribution exact method will be presented.

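### By-dose adverse-event rates put a permanent discontinuer's off-treatment follow-up into the row of the last dose received, so the dose rows are not like for like, and FU2 events may be counted without matching patient-time

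*SAP*

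**What the plan says.** Three rules in the SAP combine.

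- **Events.** Section 4.5.2 assigns an event to a dose by its onset, up to the next dose. For the phases without dosing it adds that "AEs that are reported during non-dosing phases (Follow-up 1, Follow-up 2) will be assigned to the last dose received".
- **Time.** Section 4.5.1.2 ends each dose's interval on the day before the next dose. The exception reads "With the exception of the last dose received by the patient where the date of last observation during the DBT and FU1 phases" (or, for the ocrelizumab-exposed set, the last observation in that set) is used instead.
- **Output.** Section 4.5.2: "The rates per 100 patient-years will be summarized by treatment and dose and by treatment (including all doses"). Section 4.5.4 gives infection and serious-infection rates "overall and by dose based on the number of patient-years observation for the specific dose". Section 4.5.5 also reports opportunistic infections by dose.

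On the design, SAP 1.2 states "Patients will be treated for 144 weeks (6 study drug doses, with each dose 24 weeks apart") and that patients who stop early "will continue to be followed in the FU1 phase until 144 weeks from randomization for each patient", or until the primary analysis if that comes first.

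Elsewhere the SAP uses a 24-week limit. Section 4.1 says "the time of treatment discontinuation will be defined as 24 weeks after the last dose", and the treatment-duration formula in 4.5.1.2 is capped at the last dose plus 24 weeks. Section 4.5.1.1 adds: "If a dose is completely missed instead of delayed, the next dose number will be consecutive to the previous dose received".

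In 4.5.1.2, DBT/FU1 observation time also stops at PDP OCR, OLE, FU2 entry, commercial ocrelizumab or another MS DMT. The list for the ocrelizumab-exposed set has no FU2 stop.

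**The concern.** A reader will compare the dose rows to see whether risk changes with successive dosing. Protocol 5.1.1.1 raises that question itself: immunoglobulin decreases became more common with continued dosing, and a higher serious-infection risk is not excluded. For a patient who continues on schedule, a dose interval is 24 weeks. For one who stops, the last interval also takes in whatever FU1 follow-up remains, and more remains after an early dose than after a late one. The rows then mix on- and off-treatment time in different proportions. If ocrelizumab carried a constant excess risk while on treatment, the early rows would be diluted most and the excess could appear to grow with dose number.

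A second issue concerns matching. The safety-set reporting window in SAP 4.5 ends at PDP OCR, OLE, commercial ocrelizumab or another DMT, but not at FU2. FU2 events go to the last dose, yet DBT/FU1 patient-time stops on the day before FU2. If that patient-time is the denominator for the safety set, FU2 events enter a last-dose row with no time behind them.

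**Working it through.** **Figure in the plan.** The documents give no off-treatment share by dose, no treatment-discontinuation rate and no FU1 retention rate. The nearest input is the 10% annual dropout in SAP 2.2, so I first checked how it is used there. Take exponential event times with 40% placebo progression at Week 120, dropout as censoring, 500 patients per arm, HR 0.70, and onset counted to Week 132 (144 minus 12 weeks for confirmation):

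- λ = −ln(0.60)/120 = 0.004257 per week; μ = −ln(0.90)/52 = 0.002026 per week.
- Events per arm = 500 × L/(L+μ) × (1 − exp(−(L+μ) × 132)), with L = λ for placebo and 0.70λ for ocrelizumab.
- Total 335, against the plan's approximate 340. The MRI-active subgroup gives 122.7 against 122.
- A full 144-week window gives 355 with this dropout and 404 without it.

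The plan's count fits dropout as loss from observation. Patients lost in that way add no FU1 time, so using 10% as a treatment-stopping rate is my assumption.

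**Off-treatment share by dose (DBT/FU1).** Let p be the probability of not receiving the next dose and s the fraction of stoppers observed in FU1 to Week 144 without another DMT or commercial ocrelizumab.

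- p = 1 − 0.90^(24/52) = 4.75%.
- Off-treatment weeks per Dose k recipient = p × s × (144 − 24k).
- Share = off/(24 + off).
- Dose 1 with s = 1: 0.0475 × 120 = 5.70 weeks; 5.70/29.70 = 19.2%.

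| Stop rate per year, s | Dose 1 | 2 | 3 | 4 | 5 | 6 |
|---|---|---|---|---|---|---|
| 10%, s = 1 | 19.2% | 16.0% | 12.5% | 8.7% | 4.5% | 0% |
| 10%, s = 0.5 | 10.6% | 8.7% | 6.6% | 4.5% | 2.3% | 0% |
| 10%, s = 0 | 0% | 0% | 0% | 0% | 0% | 0% |
| 5%, s = 1 | 10.5% | 8.6% | 6.6% | 4.5% | 2.3% | 0% |
| 15%, s = 1 | 26.5% | 22.4% | 17.8% | 12.6% | 6.7% | 0% |

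Across all doses, at 10% and s = 1, about 16.0 of 144 weeks (11%) are off treatment.

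**Ocrelizumab-exposed set.** FU2 time counts there. If a fraction q of Dose 6 recipients entered the 24-week FU2 instead of the OLE, the Dose 6 share would be 24q/(24 + 24q): 9.1% at q = 10% and 16.7% at q = 20% (both assumed).

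**Effect on a rate ratio.** Apparent ratio = (1 − share) × on-treatment ratio + share × off-treatment ratio, with an assumed on-treatment ratio of 1.5 and a common background rate.

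- Off-treatment ratio 1.0, s = 1: 0.808 × 1.5 + 0.192 × 1.0 = 1.40 at Dose 1; 1.50 at Dose 6.
- Off-treatment ratio 1.25, because depletion persists: 0.808 × 1.5 + 0.192 × 1.25 = 1.45 at Dose 1; 1.50 at Dose 6.
- At s = 0.5, Dose 1 gives 1.5 − 0.106 × 0.5 = 1.45 and 1.5 − 0.106 × 0.25 = 1.47.
- Off-treatment ratio also 1.5: no change in any row.

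**The case against.** The other side has several good points.

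- **Two durations are defined on purpose.** Section 4.5.1.2 separates treatment duration (capped) from duration under observation (uncapped), and 4.5.4 names observation time for the infection rates. Section 4.1 defines when treatment stops, not a risk window for adverse events. This stands: the rule is a choice, not a contradiction.
- **Off treatment is not unexposed.** Protocol 5.1.1.1 gives a median time to B-cell repletion of 72 weeks (range 27 to 175), so attribution to the last dose is defensible. This stands, and it makes the 1.45 scenario more plausible than the 1.40 one.
- **The shift would be hard to see.** Suppose the 6.2% of ocrelizumab patients with a serious infection in the previous PPMS trial carried over to about 500 patients. That is about 31 patients, or roughly 5 per dose row, and the exact Poisson 95% interval for 5 events runs from 1.6 to 11.7. The tables are descriptive, and no by-dose rate ratio is explicitly planned. This stands for serious infections; more frequent outcomes would show a shift more readily.
- **All adverse events may show the opposite trend.** Infusion-related reactions are counted and are more frequent at the first infusion, which raises the Dose 1 rate. This is true of the net picture. It does not remove the dilution, since off-treatment time adds denominator and no infusion reactions.

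A reader might infer that about 19% of Dose 1 time will be off treatment. The documents do not support that as a fact: it requires reading the sample-size dropout as treatment discontinuation with complete FU1 retention. A reader might also infer that the rates themselves must drift with dose number. Only the mix of time does so; the rate moves only where on- and off-treatment rates differ.

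**Conclusion.** The point holds as a modest comparability problem in descriptive safety tables. The allocation of events and time is explicit in the SAP, and in the DBT/FU1 by-dose rates the off-treatment share can fall with dose number. If 10% per year stop treatment, the Dose 1 share lies between 0% and about 19% depending on FU1 retention, and the Dose 6 share is 0% on schedule. The ocrelizumab-exposed set differs because FU2 time counts there. Not all off-treatment follow-up is included: in DBT/FU1 the clock stops at another MS DMT or commercial ocrelizumab.

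A difference between on- and off-treatment rates is certain for all adverse events to the extent that infusion reactions occur, and plausible but unproven for infections. The rate ratios used are assumptions.

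The FU2 mismatch is a separate gap. Numerator and denominator agree for FU1, but the text lets FU2 events enter a last-dose row without time. Its size cannot be computed, because the number of FU2 patients before the clinical cutoff is not given.

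Neither issue touches the efficacy analyses. The change is worth making because it is cheap and loses no event.

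**What to change.** In SAP 4.5.1.2 and 4.5.2:

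1. For patients who permanently discontinue study treatment, and only for them, end the last dose's interval 24 weeks after that dose, for events and time alike. This is the SAP's own treatment-duration limit. Put later events and time in a separate post-treatment follow-up row.
2. Leave the intervals of continuing patients with delayed or missed doses running to the next infusion. Capping every interval would move events that occur during a delay, including infections that caused it, into a post-treatment row for patients still on treatment. A missed dose still lengthens the preceding interval; a footnote can say so.
3. State one FU2 rule for numerator and denominator in each analysis set: either both stop at FU2 entry or both include it.
4. Keep the rate over all doses, subject only to item 3.

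Under item 1, permanent discontinuers contribute no time beyond 24 weeks to any dose row, and the dose and post-treatment rows together add back to the totals. The cost is a few lines of SAP text, one table row and minor programming. The downside is that depletion outlasts 24 weeks (median repletion 72 weeks), so the post-treatment row must be read together with the dose rows and not as an unexposed comparator.

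### The exact Poisson limits in SAP 4.5.2 are written per 1 patient-year although the rate they accompany is per 100 patient-years

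*SAP*

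**What the plan says.** SAP 4.5.2 (Adverse Events) calls for rates per 100 patient-years with 95% intervals, by treatment group, for all AEs, SAEs, infections, serious infections, opportunistic infections and malignancies. The rate is the total number of AEs divided by the total number of patient-years, multiplied by 100.

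The next bullet introduces the interval on the same scale: "The 95% confidence interval (CI) for the number of AEs per 100 patient-years will be calculated using the exact method", based on the Poisson distribution. The limits are then given as

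- lower: chisq(p = 0.025, df = 2Y) / (2T)
- upper: chisq(p = 0.975, df = 2(Y + 1)) / (2T)

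The symbols are explained as follows: "where Y is the total number of AEs, T is total number of patient-years at risk". The function chisq(p, df) "is the quantile of the upper tail probability of the Chi-squared distribution with df degrees of freedom". The SAP adds that the method still provides an upper limit when no events occur.

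Later sections rely on this formula. SAP 4.5.4 says: "The rate per 100 patient-years by treatment group (along with the 95% CI) will be calculated for infections and serious infections", overall and by dose. SAP 4.5.5 and 4.5.6 ask for the same for opportunistic infections and malignancies. None of them gives another formula. Protocol 6.5 lists rates per 100 patient-years but no formula for the limits, and SAP section 5 states that there is no additional supporting document.

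**The concern.** The point estimate carries a factor of 100 and its limits do not. T is counted in single patient-years, so it does not absorb the missing factor. A rate and an interval that share the label per 100 patient-years are therefore on different scales.

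The protocol treats infection as an identified risk and malignancy as a potential risk (5.1.1.1 and 5.1.1.2). For such events the upper limit tells a reader which rates the data do not rule out. An upper limit 100 times too low would understate that range badly. The case hardest to notice is zero events, which by-dose tables make more likely: an interval running from 0 to a very small number does not look wrong beside a rate of 0.

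**Working it through.** The documents give no numerical rate or interval, so there is no planned figure to reproduce. The check is algebraic, with a numerical illustration.

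**Inputs.** The rate, the two limits and the definitions of Y and T come from SAP 4.5.2. Event counts and patient-years are assumptions. T = 1200 per arm is a plausible size: 500 patients per arm, 144 weeks (about 2.76 years) and 10% annual dropout (SAP 2.2) give 500 × (1 − 0.9^2.76) / (−ln 0.9), or about 1200. It would be lower if the 340-event trigger came early. The scale error does not depend on T.

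**Algebra.** The exact Poisson limits for the expected count are chisq(0.025, 2Y)/2 and chisq(0.975, 2(Y+1))/2, with lower-tail quantiles. Dividing by T gives limits per 1 patient-year, which is the SAP's formula. Limits per 100 patient-years need a further factor of 100, so each limit as given is 1/100 of the right one.

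**Numbers, lower-tail quantiles, T = 1200 (2T = 2400).**

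| Events Y | Rate per 100 PY | Chi-squared quantiles | SAP formula | With factor 100 |
|---|---|---|---|---|
| 0 | 0 | 0 and 7.378 | 0 to 0.0031 | 0 to 0.31 |
| 10 | 0.83 | 9.591 and 36.781 | 0.0040 to 0.0153 | 0.40 to 1.53 |
| 80 | 6.67 | 126.87 and 199.13 | 0.053 to 0.083 | 5.29 to 8.30 |

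For Y = 10: 9.591/2400 = 0.0040, 36.781/2400 = 0.0153, and the rate is 100 × 10/1200 = 0.83.

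**Does the interval contain its own rate?** The upper limit divided by the rate is [chisq(0.975, 2(Y+1))/2] / (100Y), in which T cancels. It is largest at Y = 1, where it is 5.57/100 = 5.6%, and it stayed at or below that for every Y from 1 to 5000. With at least one event, then, the whole interval lies below the rate. With Y = 0 the interval starts at 0 and contains the rate.

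**Is the rescaled formula right?** For Y = 20 and T = 1000 it gives 1.222 to 3.089 around a rate of 2.0, and the Poisson tail probabilities at the two limits are both 0.025.

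**Effect of the stated tail.** The SAP describes chisq(p, df) by its upper tail. Taken literally, for Y = 10 and T = 1200:

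- lower = 34.170/2400 = 0.0142
- upper = 10.982/2400 = 0.0046

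The limits are reversed. Multiplying by 100 alone gives a lower limit of 1.42 and an upper limit of 0.46 around a rate of 0.83, which is not a usable interval.

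**The case against.** The strongest reply is that the intended quantity is not in doubt. The SAP names the exact Poisson method, says the interval is per 100 patient-years and shows the conversion one line above. Quantile over 2T is the standard interval per unit of person-time, so rescaling follows from the stated target. Wherever an event occurs, an unscaled interval would sit visibly below the estimate printed beside it and would probably be caught in output review. This stands: it is an error in the written specification and not evidence that wrong tables will be produced. It is weaker for zero counts, where the mismatch would not show.

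Three stronger readings are tempting, and the documents do not support them.

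- A reader might infer that every safety interval is wrong. The incidence rate ratio interval in SAP 4.5.4 has no units and is unaffected. SAP 4.5.10 names only Poisson methods for the immunoglobulin analysis and gives no formula.
- A reader might infer that every interval excludes its own rate. That fails when there are no events, a case the SAP itself mentions.
- A reader might infer that the text taken literally gives limits too low by exactly 100. That holds only with lower-tail quantiles. Under the literal upper-tail wording, for Y = 10 and T = 1200, the lower limit is too low by a factor of about 28 (0.400/0.0142) and the upper by about 335 (1.533/0.00458), and they are reversed. Under either convention both limits stay far below the rate once an event has occurred.

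**Conclusion.** The scale error is real. The limits in SAP 4.5.2 are per 1 patient-year, the rate is per 100, and nothing elsewhere in the SAP or protocol restores the factor. With lower-tail quantiles the discrepancy is exactly 100 for any number of patient-years and, for non-zero limits, any event count.

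Its reach is the set of descriptive rates that use this formula: all AEs, SAEs, infections, serious infections, opportunistic infections and malignancies, by arm and by dose. The sample size, the type I error procedure and the primary and secondary tests do not use these limits. The event counts and the 1200 patient-years are illustrative assumptions; the factor is not. The correction should be made before database lock, so that programming does not have to depart from the SAP without a record.

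**What to change.** In SAP 4.5.2, write the limits as

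- lower: 100 × chisq(0.025, 2Y) / (2T)
- upper: 100 × chisq(0.975, 2(Y + 1)) / (2T)

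or keep the formulas and define T in units of 100 patient-years. In the same edit, define chisq(p, df) as the lower-tail (cumulative) quantile, because the factor 100 alone does not give a usable interval under the present wording. It would also help to state that the lower limit is 0 when Y = 0, since the quantile then has zero degrees of freedom.

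The cost is a few words of SAP text. No data collection, sample size or other analysis changes.
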